To whom it may concern

Date : 15/06/2020

Subject : Vitamin D Regulates the Expression of Glucocorticoid Receptors in Blood of Severe Asthmatic Patients

I am [name] ,Principle investigator for the study (Vitamin D Regulates the Expression of Glucocorticoid Receptors in Blood of Severe Asthmatic Patients) . I am confirming that the document is relevant to the study in the record.

Title :Vitamin D Regulates the Expression of Glucocorticoid Receptors in Blood of Severe Asthmatic Patients

Introduction

Vitamin D (VitD) deficiency is a public health concern affecting up to 80% of the population in certain countries and of all age groups ¹. Hypovitaminosis D is prevalent in the Middle East and North Africa (MENA) ², and VitD level is suboptimal in the residents of sunny United Arab Emirates (UAE) ³. In addition to its well-established role in calcium and bone metabolism, the potential roles of VitD in cancer development, cardiovascular and chronic lung diseases are being increasingly appreciated ⁴. The increased awareness of VitD deficiency and related health problems made vitamin D supplementation a routine action plan even without laboratory confirmations leading to a higher risk of exogenous hypervitaminosis D ⁵. Black et al. were among the first to show a positive correlation between VitD status and pulmonary function ⁶. VitD deficiency is associated with features of asthma, such as decreased lung function, increased airway remodeling, and airway hyperresponsiveness ⁷. Several reports suggested the association of VitD levels with the severity of asthma ⁸. Different cross-sectional studies indicated that low serum VitD in patients with mild to moderate asthma is associated with poor asthma control, more exacerbations, reduced lung function, and increased medication use ⁹⁻¹¹. Inverse relationships have also been reported between serum VitD levels and airway remodeling, IgE, eosinophil numbers, as well as airway hyperresponsiveness. Interestingly, Gupta et al. demonstrated a role for active VitD in correcting IL-10 levels in a paediatric population of moderate and severe therapy-resistant asthma ¹². On the other hand, experimental studies demonstrated that vitamin D receptor (VDR)-deficient mice fail to develop airway inflammation (decreased infiltration of lymphocytes and eosinophils) and experimental allergic asthma ¹³.

Steroid resistance, as documented in cases of severe asthma, is associated with increased expression of the glucocorticoid receptor (GR)- β , which is an alternative splicing isoform and dominant-negative regulator of the GR- α ¹⁴. The abundance of GR- α mRNA is higher than GR- β mRNA in all normal tissues and cells. Normally, default splicing pathway leads to GR- α , while the alternative

splicing pathway that leads to GR- β is minimally activated ¹⁵. The latter pathway, however, seems to be upregulated in severe asthmatic patients ¹⁶. In chronic inflammatory diseases like asthma, upregulated blood levels of inflammatory cytokines can participate in glucocorticoid resistance and impaired GR function by modulating its translocation, DNA binding, and GR phosphorylation status [18].

As data from observational studies suggested a better control of asthma following restoration of VitD levels.

Hypothesis:

Correcting VitD levels in adult asthmatic patients could enhance steroid responsiveness by regulating blood GR- α /GR- β ratio levels.

Primary Out comes:

1. To find out the top pathways regulate Vitamin D

identify VitD targeted enriched pathways, we analyzed Comparative Toxicogenomics .Enriched Ontology Clustering for the identified genes was performed using the Metascape (a web-based tool used for comprehensive gene list annotation and analysis resource)Database from thousands of experiments.[Time Frame: 8 weeks]

2. To examine asthma severity in relation to steroid receptors genes [Time Frame: 8 weeks]

3. study the effect of vitamin D on GR- α receptor [Time Frame: 8 weeks]

4. study the effects of Vitamin D on cytokines. [Time Frame: 8 weeks]

Inclusion Criteria:

- Diagnosis of asthma
- age group between 18 and 65 years
- low level of 25-hydroxyvitamin D3 (25 D3) level less than 20ng/mL

Exclusion Criteria:

- smoker patients
- less than 18 years old
- patient on Vitamin D supplementation already

Materials and Methods

In silico identification of top genes regulated by vitamin D supplementation

Using Comparative Toxicogenomics Database to identify the top genes influenced by vitamin D supplementation in thousands of experiments. One hundred five genes with at least five documented interactions with VitD were identified. Moreover, to explore if the identified genes are sharing common pathways, Enriched Ontology Clustering for the identified genes will be performed using the Metascape (a web-based tool used for comprehensive gene list annotation and analysis resource).

In silico determination of effect of vitamin D treatment on the expression of NR3C1 and NR3C2 in monocytes, macrophages, and dendritic cells

In order to investigate the effect of VitD supplementation on the mRNA expression of NR3C1, NR3C2 and VDR, publicly available datasets (GSE52819, GSE13762, GSE56490) will be explored as they were designed to examine the global transcriptional effect of VitD supplementation on monocytes, macrophages, and dendritic cells.

In silico determination of the mRNA expression levels, and correlations, of NR3C1, NR3C2, and VDR in the blood of asthmatic patients compared to healthy controls

We will extract from publicly available datasets (GSE69683) with a large number of participants and their detailed clinical information. To find Gene expression profiling of blood from these groups was analyzed, and the gene expression of GR (NR3C1 and NR3C2) which was determined.

Patients

To do double-blinded, randomized, placebo-controlled study of VitD supplementation on 45 asthmatics with VitD deficiency will be performed. Moderate to severe asthmatics between 18 and 65 years of age who had clinician-diagnosed asthma with 25-hydroxyvitamin D3 (25 D3) level less than 20ng/mL at the screening visit will be recruited at the Rashid Hospital, Dubai, U.A.E., and the Zayed Military Hospital, Abu Dhabi, U.A.E.

mRNA expression and cytokine expression

Whole blood will be collected in PAXgene tubes (Qiagen, Germany) for the isolation of cellular RNA. Blood specimens will be assessed for mRNA expression of Glucocorticoid receptor (GR- β and

GR- α) using qRT-PCR. Bioplex multiplex immunoassay (BioRad, CA, USA) will use to assess the protein expression of IL-17A, IL-17-F, IFN- γ , IL-4, IL-5 and TNF- α in serum obtained from patients before and after treatment.

Statistical Analysis

Standard statistical t-tests and one-way ANOVA will be performed to test for statistical significance between data groups using GraphPad Prism 8 (GraphPad, San Diego, CA, USA). $p < 0.05$ was considered significant.

To whom it may concern

Date : 15/06/2020

Subject : Vitamin D Regulates the Expression of Glucocorticoid Receptors in Blood of Severe Asthmatic Patients

I am [name] ,Principle investigator for the study (Vitamin D Regulates the Expression of Glucocorticoid Receptors in Blood of Severe Asthmatic Patients) . I am confirming that the results is relevant to the study in the record.

Results :

Top Vitamin D regulated pathways are involved in response to Steroids

To identify VitD targeted enriched pathways, we analyzed Comparative Toxicogenomics Database from thousands of experiments. Interestingly, the top enriched pathways regulated by VitD were involved in several metabolic and inflammatory processes including response to steroids, lipopolysaccharide as well as Interleukin-4, Interleukin-13 and AGE-RAGE signalling (Suppl. Figure 1). Many of those VitD targeted pathways were also targets of dexamethasone. These include pathways involved in inflammation; proliferation; pro-apoptosis, beside others (Figure S1).

VDR, NR3C1 and NR3C2 expression levels in different types of immune cells

The level of expression of GR coding gene (NR3C1), mineralosteroid receptor coding gene (NR3C2)¹⁷, and VDR were then determined in different immune cells. NR3C1 had a significantly higher level of expression compared to VDR and NR3C2 in different types of immune cells (Figure 1). Among all cells, its expression was significantly higher on Th2 CD4 cells (215.9 TPM). Classical (94.5 TPM) and non-classical monocytes (46.7 TPM) had the highest VDR expression among all inflammatory cells. Moreover, the expression of all three genes was higher in non-classical monocytes compared to classical ones (2.0, 1.49, and 1.21 folds, respectively). Naïve CD8 T (74.1 TPM) cells and Th1/17 CD4 cells on the other hand (64.7 TPM) had the highest NR3C2 mRNA expression among all immune cells. On the other hand, activation of T cells seems to induce the expression of VDR and NR3C1, but not NR3C2 genes. Activated CD8 T cells express higher VDR and NR3C1 (10.6 and 1.47 respectively) and lower NR3C2 (0.12-fold), compared to naïve cells. Similarly, activated CD4 T cells express higher VDR, and NR3C1 (3.95 and 1.25 respectively) and lower NR3C2 (0.11-fold), compared to naïve CD4 T cells (Figure 1).

[figure not shown]

Figure 1: NR3C1, NR3C2 and VDR mRNA expression level in immune cells. Data was extracted using publicly available “Database of Immune Cell Expression, Expression quantitative trait loci (eQTLs) and Epigenomics”.

VDR and steroid receptors genes are downregulated in asthma relative to severity

Activated T cells was shown to upregulate VDR, while treatment with VitD suppressed the proliferation of these cells, as well as their ability to produce IFN- γ and IL-17 cytokines.¹⁸ The level of expression of VDR in the blood of asthmatic and its association with the expression of steroid receptors relative to disease severity was not determined. To investigate that, we analyzed the expression profile of publicly available datasets (GSE69683) which has a large number of participants and detailed clinical information. A total number of 498 participants, of which 87 healthy controls, 77 moderate asthma, and 246 non-smokers severe asthma were included in the U-BIOPRED study. The differential expression of NR3C1, NR3C2, and VDR genes in the blood of patients from all groups was then determined. Patients with moderate asthma had higher levels of NR3C1 mRNA expression compared to health controls, although not to a significant level (\log_2 intensity 10.17 ± 0.29 ; $p=0.07$) (Figure 2A). When compared to moderate asthmatics, the expression of this gene, however, was significantly downregulated in severe asthmatic (\log_2 intensity 10.14 ± 0.23 versus 10.26 ± 0.21 ; $p<0.01$). NR3C2 mRNA expression was significantly downregulated in severe asthmatic compared to moderate asthma (\log_2 intensity 5.397 ± 0.727 versus 5.62 ± 0.5011 , $p<0.01$), and to healthy controls (\log_2 intensity 5.575 ± 0.5894 versus 5.397 ± 0.727 , $p=0.03$) (Figure 2B). Moderate asthmatics showed higher NR3C2 mRNA expression than healthy controls, although the difference was not significant. On the other hand, VDR mRNA expression was significantly upregulated in severe asthmatics compared to healthy controls (\log_2 intensity 8.386 ± 0.46 versus 8.206 ± 0.44 $p<0.01$), but not to moderate asthmatics (Figure 2C). Interestingly, NR3C1 mRNA expression correlated positively (Spearman $r = 0.11$, 95% confident interval=0.02007 to 0.1988 and $p = 0.01$) (Figure 2D), while NR3C2 expression correlated

negatively (Spearman $r = -0.55$, 95% confident interval = -0.5724 to -0.438 and $p < 0.0001$) with the levels of VDR expression in blood (Figure 2E).

[figure not shown]

Figure 2: NR3C1, NR3C2 and VDR mRNA expression level in the blood of subjects with severe asthma, moderate asthma, and non-asthmatics. Data was collected in the U-BIOPRED study (GSE69683).

Supplementation of vitamin D selectively favours the upregulation of GR- α receptor

To validate the *in silico* findings, a double-blinded, randomized, placebo-controlled study was performed to test the effect of VitD supplementation on 45 vitamin D deficient asthmatics. Moderate to severe asthmatics between 18 and 65 years of age who were diagnosed with asthma and VitD (25D3) levels less than 20ng/mL at the screening visit were recruited at two hospitals in UAE (Rashid Hospital, Dubai, U.A.E. and Zayed Military Hospital, Abu Dhabi, U.A.E.). The patients were divided into two groups, an experimental group and a placebo group. The baseline serum levels of VitD in the experimental and placebo groups were comparable (11.74 ± 0.77 ng/mL, 12.96 ± 1.29 ng/mL, respectively). The experimental group received 50, 000 IU of VitD

oral supplementation weekly for eight weeks ¹⁹. Following treatment, a 2.84 ± 0.01 -fold increase in blood VitD D levels (33.34 ± 2.04 ng/mL) was observed (Figure 3). The level of VitD in the placebo group did not change (14.45 ± 1.61 ng/mL) (Table 1 and Figure 3). This result indicated that the regimen used was effective to correct VitD deficiency.

Table 1: Clinical characteristics of patients received vitamin D or placebo for eight weeks.

| Variable | Total | Placebo | Vitamin D |
|--|------------------|------------------|------------------|
| Total | 54 | 20 | 34 |
| Male | 19 (35%) | 4 (20%) | 15 (44%) |
| Female | 35 (64.8%) | 16 (80%) | 19 (55.8%) |
| Age (years) | 38.64 ± 1.90 | 40.60 ± 2.97 | 37.45 ± 2.48 |
| Body Mass Index | 32.27 ± 0.92 | 32.32 ± 5.52 | 32.32 ± 1.28 |
| Pre-treatment 25D₃ levels (ng/mL) | | 12.96 ± 1.29 | 11.74 ± 0.77 |
| Post treatment 25D₃ levels (ng/mL) | | 14.45 ± 1.61 | 33.34 ± 2.04 |

[figure not shown]

Figure 3: Pre-treatment and post-treatment levels of serum vitamin D (25D3) in patients who received vitamin D or placebo for eight weeks. Severe asthmatic patients with vitamin deficiency were divided into 2 groups. 23 patients received 50000 IV of Vitamin D orally over 8 weeks, while 22 patients received placebo. Vitamin D levels were measured in the blood of these patients before and after the treatment.

We next determined whether VitD supplementation affects the gene expression of steroid receptor GR- α or GR- β . Correction of VitD levels lead to a significant increase in the expression of GR- α

when compared to baseline level. A significant increase was observed following treatment with VitD compared to pre-treatment levels (1.89 ± 0.56 , 5.34 ± 1.40 , respectively; $p<0.05$) (Figure 4A). Moreover, there was a significant increase in GR- α expression in patients who received VitD compared to those who received the placebo control (5.34 ± 1.40 versus 1.64 ± 0.76 -fold; $p<0.05$). Interestingly, no change in GR- β expression was observed following treatment with VitD (1.49 ± 0.27 versus 1.30 ± 0.25) (Figure 4B). Relatively, the GR- α /GR- β ratio increased significantly following VitD supplementation compared to pre-treatment levels (3.58 ± 0.83 folds; $p<0.05$); or patients who received a placebo (Figure 4C).

[figure not shown]

Figure 4: Vitamin D treatment increases the expression of GR- α with no effect on GR- β .

Asthmatic subjects were treated with 50,000 IU of vitamin D orally or placebo for eight weeks. Blood specimens obtained following 8 weeks of treatment were analyzed for mRNA expression of GR- α (A), GR- β (B) using RT qPCR and the ratio of GR- α /GR- β was calculated (C). * $p<0.05$

Vitamin D supplementation downregulated the blood levels of IL-17 and IL-4 cytokines in asthmatic patients

The effect of VitD supplementation on the blood levels of asthma related pro-inflammatory cytokines was then determined (Figure 5)²⁰. Blood levels of IL-17A, IL-17F, IFN- γ , IL-4, IL-5, and TNF- α were determined before and after VitD supplementation using ELISA assay (Figure 5). VitD preferentially suppressed the blood levels of IL-17F cytokine ($p=0.04$) without affecting IL-17A; while there was no significant difference in the placebo group ($p=0.17$). A decrease in blood IL-4 cytokine levels was observed following treatment, however, not to a significant level ($p=0.07$). No significant effect of VitD supplementation was observed on the rest of the cytokines tested.

References

- 1 Palacios, C. & Gonzalez, L. Is vitamin D deficiency a major global public health problem? *J Steroid Biochem Mol Biol* **144 Pt A**, 138-145, doi:10.1016/j.jsbmb.2013.11.003 (2014).

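### The blood comparison for primary outcome 2 cannot exclude cell mix as a source of the VDR and NR3C2 differences that the results read as gene regulation

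*Combined protocol and SAP*

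**What the plan says.** Primary outcome 2 is to examine asthma severity in relation to the steroid-receptor genes. The GSE69683 subsection of Materials and Methods describes the comparison as "Gene expression profiling of blood from these groups was analyzed, and the gene expression of GR (NR3C1 and NR3C2) which was determined". The Statistical Analysis section gives the method for the whole study: "Standard statistical t-tests and one-way ANOVA will be performed to test for statistical significance between data groups", with a 0.05 threshold. Neither place mentions differential counts, estimated cell fractions, covariates or a caveat about cell composition.

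The Results section reports the comparison for "87 healthy controls, 77 moderate asthma, and 246 non-smokers severe asthma". It uses the language of regulation throughout, for example "NR3C2 mRNA expression was significantly downregulated in severe asthmatic compared to moderate asthma". It also reports Spearman correlations with VDR in blood of 0.11 for NR3C1 and -0.55 for NR3C2.

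Just before that, the Results subsection on immune-cell types (Figure 1) shows how far the three genes depend on the cell measured. It states "Activated CD8 T cells express higher VDR and NR3C1 (10.6 and 1.47 respectively) and lower NR3C2 (0.12-fold", relative to naive cells. For CD4 cells the corresponding ratios are 3.95 (VDR), 1.25 (NR3C1) and 0.11 (NR3C2). VDR is highest in monocytes, and NR3C2 in naive CD8 T and Th1/17 CD4 cells.

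**The concern.** Expression measured in mixed-cell blood is an average over the cells present, weighted by how many there are and how much each expresses. A difference between severity groups can therefore arise because cells express more or less of the gene, because the mix of cells differs, or both. An unadjusted comparison of means does not separate these.

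This matters most for a gene whose expression varies widely between cells when the group difference is small. By the document's own figures, VDR and NR3C2 are in that position. At stake is the wording of the conclusion on a stated primary outcome. The data support a difference in blood transcript level; the claim that the receptor genes are regulated with severity needs a further step that the plan does not contain.

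**Working it through.** **Inputs.** Means, spreads and group sizes come from the Results subsection on severity (Figure 2), and cell-type figures from the subsection on immune cells (Figure 1). I assume that ± is a standard deviation, that tests are two-sided, and that group sizes are 246 severe, 77 moderate and 87 healthy. These sum to 410; the other 88 of the 498 participants are not described.

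**1. Reproducing the stated tests.** For NR3C1, severe versus moderate ("10.14 ± 0.23 versus 10.26 ± 0.21"):

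- Pooled SD = √[(245 × 0.23² + 76 × 0.21²)/321] = 0.225.
- Standard error = 0.225 × √(1/246 + 1/77) = 0.0294.
- t = -0.12/0.0294 = -4.1, p about 0.00006. The stated p<0.01 is reproduced.

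**2. Size of the significant differences.** Ratio = 2^(difference in log2 means).

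| Contrast | log2 difference | Ratio | Change | p, Student / Welch | Stated p |
|---|---|---|---|---|---|
| NR3C1, severe vs moderate | -0.120 | 0.920 | -8.0% | 0.00006 / 0.00004 | <0.01 |
| NR3C2, severe vs moderate | -0.223 | 0.857 | -14.3% | 0.013 / 0.003 | <0.01 |
| NR3C2, severe vs healthy | -0.178 | 0.884 | -11.6% | 0.041 / 0.024 | 0.03 |
| VDR, severe vs healthy | +0.180 | 1.133 | +13.3% | 0.002 / 0.001 | <0.01 |

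The NR3C2 p-values depend on which t-test is used, but all four contrasts are below 0.05 either way.

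**3. Dependence on cell type and state.**

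- VDR: activated-to-naive ratio 10.6 (CD8) and 3.95 (CD4); highest in monocytes.
- NR3C2: 0.12 (CD8) and 0.11 (CD4), that is 1/0.12 = 8.3 and 1/0.11 = 9.1 times lower in activated cells.
- NR3C1: 1.47 (CD8) and 1.25 (CD4). Monocyte-subset ratios for the three genes are 1.21 to 2.0, so no ratio given for NR3C1 exceeds 2.0.

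For VDR and NR3C2, the variation between cells is far larger than the 12-14% group differences.

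**4. Direction.** More activated T cells in a sample would mean higher VDR, lower NR3C2 and slightly higher NR3C1. The first two match severe versus healthy blood and the correlation of -0.55. The third matches the weak positive NR3C1-VDR correlation (0.11) but not the 8% NR3C1 fall in severe versus moderate asthma.

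**5. Does one simple shift fit all three genes?** Take a mix that starts all naive and move a share s to activated. Expression of each gene then changes by s × (f - 1), where f is the activated-to-naive ratio.

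- Severe vs moderate: NR3C2 needs s = 0.143/0.88 = 0.163 (CD8) or 0.143/0.89 = 0.161 (CD4). The same s predicts VDR up by 0.161 × 2.95 = 47% to 0.163 × 9.6 = 156%; no significant difference is reported. It predicts NR3C1 up by 0.161 × 0.25 = 4% to 0.163 × 0.47 = 8%; it is reported 8% lower.
- Severe vs healthy: NR3C2 needs s = 0.116/0.88 = 0.132 or 0.116/0.89 = 0.130. VDR is then predicted up by 0.130 × 2.95 = 38% to 0.132 × 9.6 = 127%; the reported rise is 13%.

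No single shift of this kind fits. The adjusted differences cannot be computed, because the document gives neither cell counts nor patient-level data.

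**The case against.** A reader might infer that cell mix explains the severity results and that a small naive-to-activated shift would be enough. The documents do not support that. Step 5 shows that a shift fitted to NR3C2 overshoots VDR and moves NR3C1 the wrong way. Fitting VDR alone gives a small shift only if all VDR signal starts in naive T cells, whereas the document puts VDR highest in monocytes. It gives no leukocyte fractions for any group. No percentage shift should therefore be quoted as an explanation.

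The largest ratios also compare states of one lineage, and the document describes activation as inducing VDR and NR3C1. Part of what looks like mix may thus be regulation within cells. That stands, and it limits how an adjusted result can be read. Leukocyte changes may themselves belong to severe disease, so adjustment can remove part of a true association.

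Primary outcome 2 is worded as an association, and an unadjusted blood difference answers it. That stands too: the unadjusted comparison is valid as a description. Only its reading as regulation goes beyond the analysis.

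Finally, a reader might extend the point to the trial's GR-α endpoint, since "Whole blood will be collected in PAXgene tubes (Qiagen, Germany) for the isolation of cellular RNA". It does not carry over. That comparison is randomised, and a change in composition after treatment would be part of the treatment effect on blood, not a confounder. The ratios given are also for the NR3C1 gene, not the GR-α isoform.

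**Conclusion.** The point holds as a limit on interpretation. The reported severity differences are 8.0% to 14.3%, and the planned t-tests and ANOVA cannot exclude cell mix as a source of the VDR and NR3C2 differences or of their inverse correlation. For NR3C1 the case is weaker: the ratios given are at most 2.0, and T-cell activation would raise it, not lower it.

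This rests on reading ± as SD for the p-values (the percentages do not need it) and on the GSE69683 samples being mixed-cell blood. The document says blood for that dataset and writes whole blood only for the trial samples; the argument holds for any mixed-cell blood sample. It is not shown that composition differs between the groups or that the results are confounded. The point is worth acting on because it touches a stated primary outcome and the remedy uses existing public data.

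**What to change.** In GSE69683, repeat each group comparison as a linear model of log2 expression on group with leukocyte fractions as covariates, and repeat each VDR correlation as a partial Spearman correlation given the same fractions. Use recorded differential counts if the clinical file has them, which cannot be seen from the document. Otherwise estimate fractions from the same array. Include monocytes and, where they can be estimated, naive and activated T-cell subsets; broad counts of neutrophils, lymphocytes, monocytes and eosinophils alone cannot capture a shift between T-cell states.

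Report adjusted results beside the unadjusted ones, labelled as a sensitivity analysis, and add this to the Statistical Analysis section. Where a difference does not survive, describe it as a difference in blood transcript level and not as regulation. When revising the wording, also reconcile the severity subsection's heading, which counts VDR among the downregulated genes, with its text, which reports VDR higher in severe asthma than in healthy controls.

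The cost is analysis time, error in the estimated fractions, a few degrees of freedom among 410 participants in the three described groups, and the possible removal of part of a true severity association. The last is why the unadjusted results should stay in the report.

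### The plan commits to no vitamin D versus placebo contrast for the cytokines and leaves the baseline serum unused; the reported IL-17F claim rests on one p-value per arm, which cannot establish an arm effect.

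*Combined protocol and SAP*

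**What the plan says.** The plan for testing is one sentence in Statistical Analysis: "Standard statistical t-tests and one-way ANOVA will be performed to test for statistical significance between data groups using GraphPad Prism 8", with significance at p < 0.05. It does not say which groups are compared for which endpoint, whether tests are paired, or whether baseline enters the comparison.

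The fourth primary outcome is to "study the effects of Vitamin D on cytokines". Under the mRNA and cytokine expression heading, six cytokines are measured "in serum obtained from patients before and after treatment", so each patient's baseline is meant to be available. The Patients section describes a randomised, double-blind, placebo-controlled design.

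The Results section is in the same document. Its cytokine subsection is headed "Vitamin D supplementation downregulated the blood levels of IL-17 and IL-4 cytokines in asthmatic patients". The text beneath says that vitamin D preferentially "suppressed the blood levels of IL-17F cytokine ($p=0.04$) without affecting IL-17A; while there was no significant difference in the placebo group ($p=0.17". On IL-4 it says: "A decrease in blood IL-4 cytokine levels was observed following treatment, however, not to a significant level ($p=0.07". Figure 5 is not available in the text we have.

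For GR-alpha the Results do compare the arms: vitamin D patients are "compared to those who received the placebo control (5.34 ± 1.40 versus 1.64 ± 0.76 -fold; $p<0.05". The GR-alpha/GR-beta ratio is also claimed against both references: "compared to pre-treatment levels (3.58 ± 0.83 folds; $p<0.05$); or patients who received a placebo (Figure 4C".

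**The concern.** Finding p < 0.05 in one arm and p > 0.05 in the other is not a test of the difference between arms. The placebo group is there to supply that difference. Regression to the mean, season, assay drift or better adherence to asthma treatment can move both arms, and a before-after test in one arm cannot separate these from vitamin D.

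The one-sentence plan did not prevent this for a primary outcome. The text gives no IL-17F estimate in either arm, no direction for the placebo change and no between-arm p-value. The subsection heading then goes further than its own text: it names IL-4, which the text calls non-significant, and IL-17 without qualification, although IL-17A is reported as unaffected. At stake is whether the trial can claim any cytokine effect of vitamin D.

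**Working it through.** The documents contain no planned figure to reproduce. The check asks what the two printed IL-17F p-values imply about a between-arm test of change.

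**Inputs.** p=0.04 (vitamin D) and p=0.17 (placebo), from the cytokine subsection of Results. Arm sizes conflict, so both are used: 23 vitamin D / 22 placebo (Figure 3 legend) and 34 / 20 (Table 1).

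**Assumptions, not in the documents.** Both p-values are two-sided paired t-tests. The ratio r of the placebo SD of change to the vitamin D SD of change lies between 0.5 and 2.

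**Step 1: from p to change.** |t| is the two-sided t quantile on n − 1 df, and each arm's change in its own SD units is |t|/√n.
- 23/22: t = 2.183 and 1.421, so the changes are 0.455 and 0.303 SD.
- 34/20: t = 2.138 and 1.426, so the changes are 0.367 and 0.319 SD.

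**Step 2: between-arm test.** In vitamin D SD units, T = (d1 − s·r·d2) / √(1/n1 + r²/n2) with Welch df. Here s = 1 if placebo also fell and s = −1 if it rose. The case s = 0 (placebo unmoved) is a benchmark only, because p=0.17 itself implies some movement.

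Example, 23/22 and r = 1: the denominator is √(1/23 + 1/22) = 0.298. If placebo fell, T = (0.455 − 0.303)/0.298 = 0.51 and p = 0.61. If it rose, T = (0.455 + 0.303)/0.298 = 2.54 and p = 0.015.

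| Arms | r | placebo fell | unmoved | placebo rose |
|---|---|---|---|---|
| 23/22 | 0.5 | 0.20 | 0.06 | 0.014 |
| 23/22 | 1 | 0.61 | 0.13 | 0.015 |
| 23/22 | 2 | 0.75 | 0.35 | 0.033 |
| 34/20 | 0.5 | 0.32 | 0.08 | 0.013 |
| 34/20 | 1 | 0.87 | 0.20 | 0.020 |
| 34/20 | 2 | 0.58 | 0.45 | 0.046 |

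If placebo fell, p reaches 1.00 where the two changes coincide (r near 1.50 at 23/22, near 1.15 at 34/20). The ranges over r are therefore 0.20 to 1.00, 0.06 to 0.45, and 0.013 to 0.046.

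**Step 3: how often the pattern arises with no arm difference.** If both arms truly change by the same d SD, the chance of vitamin D significant and placebo not is P1 × (1 − P2), where P1 and P2 are the powers of the two paired t-tests (noncentral t, two-sided 0.05).

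| d (SD) | 0 | 0.1 | 0.2 | 0.3 | 0.4 | 0.5 |
|---|---|---|---|---|---|---|
| 23/22 | 4.75% | 6.9% | 12.9% | 20.5% | 25.5% | 24.6% |
| 34/20 | 4.75% | 8.1% | 17.7% | 29.9% | 37.4% | 35.2% |

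A direct between-arm test would reject 5% of the time throughout.

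**Step 4: IL-4.** Read the same way, p=0.07 gives a change of 0.397 SD (23/22) or 0.321 SD (34/20). With placebo unmoved and r = 1, T = 0.397/0.298 = 1.33 (p = 0.19), or 0.321/0.282 = 1.14 (p = 0.26). No placebo figure is given for IL-4.

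A baseline-adjusted result cannot be computed, because no cytokine means, SDs or changes are printed.

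**The case against.** *The plan is vague; it does not lack an arm comparison.* This stands. A reader might infer that no vitamin D versus placebo test was planned or done for any trial endpoint. The documents do not support that: the planned wording can cover an unadjusted arm comparison, GR-alpha is compared with placebo, and the ratio is claimed against placebo. The point is limited to the absence of a commitment for the cytokines.

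*Baseline adjustment is a preference.* Largely so. In a randomised trial an unadjusted week-8 comparison is valid, and the GR-alpha comparison is not at fault on this ground. ANCOVA gains precision from serum that is already planned. The defect is inference from two separate p-values.

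*The p=0.04 is not labelled as a before-after test, and Figure 5 might show more.* True. The reading follows from context: the text describes levels before and after supplementation and gives placebo a p-value of its own. A figure could supply the placebo direction or an arm comparison, but it would not supply the missing plan.

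*The magnitudes depend on assumptions.* They do, which is why ranges are shown. With no change in either arm the one-arm-only pattern is no more common than 5%. It becomes misleading when both arms drift.

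*The sharpest evidence is in results, not in the plan.* Also true, so any re-analysis is post hoc. The IL-4 heading is a reporting inconsistency that needs correcting whatever analysis is used.

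**Conclusion.** The concern holds in this limited form. The plan commits to no between-arm contrast for a primary outcome and does not use the baseline serum, and the IL-17F and IL-4 claims are not supported by the reported text. Assuming paired t-tests and SD ratios of 0.5 to 2, the implied between-arm IL-17F p runs from about 0.013 to 1.00, and the unreported placebo direction decides which side of 0.05 it falls on.

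A reader might infer that vitamin D has no effect on IL-17F. That does not follow: if placebo rose, every case examined is below 0.05. A reader might also infer that the GR-alpha result is invalid. That does not follow either; its unadjusted arm comparison is a legitimate use of the randomisation.

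The change should be made, since it decides what can be concluded about the cytokines. Confidence is medium, because the tests are not labelled, Figure 5 is not available and the arm sizes conflict.

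**What to change.** Add to Statistical Analysis: *Each cytokine (log scale) at week 8 is compared between vitamin D and placebo by ANCOVA adjusted for the patient's baseline value and reported as a geometric-mean ratio with 95% CI. Within-arm tests are descriptive only. P-values across the six cytokines are multiplicity-adjusted (for example Holm) or labelled exploratory.* The last sentence matters: six independent null tests at 0.05 give 1 − 0.95⁶ = 26% chance of at least one false positive.

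Apply the same model to GR-alpha and the per-patient GR-alpha/GR-beta ratio where baseline was assayed in both arms, as an efficiency gain only. The text prints a GR-alpha baseline for vitamin D but none for placebo.

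Make no IL-17F or IL-4 claim, in text or heading, unless the between-arm comparison supports it. Label the re-analysis post hoc, and reconcile the arm sizes (23/22 versus 34/20) before running it.

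**Cost.** A few sentences and a re-run on existing data; no new cytokine samples, because before-and-after serum is already planned. The downsides are that the analysis is post hoc, that a geometric-mean ratio is a different quantity from a difference in arithmetic means, and that values below detection need a stated rule before logs are taken.
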